Smoking duration (years) at start of first-line treatment

It will be calculated:

- For previous smokers (ie. patients with “Smoking status” [**SM.SM_status**] = “Previous smoker”): if smoking start year is not missing & smoking stop year is not missing, it will be calculated as Stop year [**SM.SM_stop_yyyy**] - Start year [**SM.SM_start_yyyy**]
- For current smokers (ie. patients with “Smoking status” [**SM.SM_status**] = “Current smoker”): if smoking start year is not missing, it will be calculated as YEAR(Start date of first-line therapy, as defined before) - Start year [**SM.SM_start_yyyy**]

BMI at start of first-line treatment

Considering the [**First-line treatment period**] time period, it will be computed as “Weight” (in Kg) [**CCPE.CCPE_weight_num, CCPE_weight_unit**] / “Height” (in centimeters) [**CCPE.CCPE_height_num, CCPE_height_unit**] * 100) ^ 2

In case weight is not reported in kg, a conversion will be performed; in case height is not reported in cm, a conversion will be performed.

BMI will also be reported as classes: underweight: BMI < 18.5, normal weight: BMI 18.5-24.9, overweight: BMI 25-29.9, obese: BMI >= 30.

Changes in ECOG PS at start of osimertinib from start of afatinib

Considering patients of the SEQUENCING COHORT with known ECOG PS both at afatinib start and at osimertinib start (ie. those with [**First-line treatment period / CCPE. CCPE_ECOG**] ≠ UNK AND [**Second-line treatment period / CCPE. CCPE_ECOG**] ≠ UNK), the difference in ECOG PS between [**Second-line treatment period**] and [**First-line treatment period**] will be computed, and the following patients groups will be defined:

- **No changes**: difference in ECOG PS = 0;
- **Improvements**: difference in ECOG PS < 0;
- **Deteriorations of 1 step**: difference in ECOG PS = 1;
- **Deterioration of 2 or more steps**: difference in ECOG PS ≥ 2.

Changes in ECOG PS at start of second-line treatment with respect to start of first-line treatment

See previous algorithm, which will be applied for UNCOMMON MUTATION COHORT.

Sites of metastases at first-line treatment start

Considering the **[First-line treatment period]** time period,

- patients with “Presence of any metastases?” **[CCPE. CCPE_met_YN]** = “No” will be classified as patients with “No metastases”;
- patients with “Presence of any metastases?” **[CCPE. CCPE_met_YN]** = “Yes” will be classified according to the options selected in field **[CCPE. CCPE_met_site, CCPE_met_site_sp]**;

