4.1.2 Demographic and clinical characteristics

Table 4-UNC. Socio-demographics (ELIGIBLE PATIENTS of the Uncommon Mutation Cohort)

The table will provide:

- descriptive statistics (mean, standard deviation, quartiles, min, max) of “Age at start of first-line treatment” [[PI. PI_age](#)];
- patients’ distribution (absolute and relative frequency) by “Gender” [[PI. PI_gender](#)];
- patients’ distribution (absolute and relative frequency) by “Ethnicity” [[PI. PI_ethn](#), [PI.ethn_sp](#)], including also those cases when ethnicity was not provided (according to the field [[PI. PI_cons_ethn_YN](#)] = “No”).

Descriptives and percentages will be calculated over the number of ELIGIBLE PATIENTS in the cohort.

Table 5-UNC. Physical examination and smoking habits at start of first-line treatment (ELIGIBLE PATIENTS of the Uncommon Mutation Cohort)

The table will provide:

- patients’ distribution (absolute and relative frequency) by classes of BMI at start of first-line treatment (see “Computed variables” chapter)
- patients’ distribution (absolute and relative frequency) by “Smoking status” [[SM. SM_status](#)];
- descriptive statistics (mean, standard deviation, quartiles, min, max) of “Estimated amount of cigarettes consumed on average each day” [[SM. SM_cig_num](#)];
- descriptive statistics (mean, standard deviation, quartiles, min, max) of smoking duration (years) at start of first-line treatment (see “Computed variables” chapter)

Descriptives and percentages will be calculated over the number of ELIGIBLE PATIENTS in the cohort.

Table 6-UNC. Clinical characteristics (ELIGIBLE PATIENTS of the Uncommon Mutation Cohort)

The table will provide:

- patients’ distribution (absolute and relative frequency) by “Patient’s ECOG Performance Status” at start of first-line treatment [[First-line treatment period / CCPE. CCPE_ECOG](#)]
- patients’ distribution (absolute and relative frequency) by “Patient’s ECOG Performance Status” at start of second-line treatment [[Second-line treatment period / CCPE. CCPE_ECOG](#)], considering only patients with Number of NSCLC treatment lines >1 (see “Computed variables” chapter)
- patients’ distribution (absolute and relative frequency) by changes in ECOG PS at start of second-line treatment with respect to start of first-line treatment (see “Computed variables” chapter), considering only patients with Number of NSCLC treatment lines >1 (see “Computed variables” chapter).

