4.2.2 Demographic and clinical characteristics

Table 4-SEQ. Socio-demographics (ELIGIBLE PATIENTS of the Sequencing Cohort)

See corresponding table for the UNCOMMON MUTATION COHORT.

Table 5-SEQ. Physical examination and smoking habits at start of first-line treatment (afatinib) (ELIGIBLE PATIENTS of the Sequencing Cohort)

See corresponding table for the UNCOMMON MUTATION COHORT.

Table 6-SEQ. Clinical characteristics (ELIGIBLE PATIENTS of the Sequencing Cohort)

See corresponding table for the UNCOMMON MUTATION COHORT.

Table 7-SEQ. NSCLC features (ELIGIBLE PATIENTS of the Sequencing Cohort)

See corresponding table for the UNCOMMON MUTATION COHORT.

In this table, the “Duration of NSCLC until start of index EGFR-TKI therapy” will be renamed as “Duration of NSCLC until start of second-line treatment” (since the index EGFR-TKI of the Sequencing cohort corresponds to the osimertinib treatment, which is also the second-line treatment by definition).

Table 8-SEQ. Sites of metastases (ELIGIBLE PATIENTS of the Sequencing Cohort)

See corresponding table for the UNCOMMON MUTATION COHORT.

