- R-DMS will perform an overall conceptual review of results, in order to evaluate their coherence and plausibility. Moreover, all the tables in this report will be independently reviewed to verify their consistency.
- Moreover, the following tables will be reprogrammed or independently verified (by another [REDACTED], as detailed for each point):

For UNCOMMON MUTATION COHORT report:

- Table 1-UNC. Patient disposition (ENROLLED PATIENTS of the Uncommon Mutation Cohort): [REDACTED]/another BS will independently recalculate frequencies
- Table 2-UNC. Reasons for violations (ENROLLED PATIENTS of the Uncommon Mutation Cohort): [REDACTED]/another BS will independently recalculate frequencies and check the algorithms for each criterion for 100% of enrolled patients
- Table 8-UNC. Sites of metastases (ELIGIBLE PATIENTS of the Uncommon Mutation Cohort): [REDACTED]/another BS will independently recalculate descriptive statistics and check the algorithm for 10% of analyzed patients
- Table 10-UNC. Approaches for detection of mutations at first-line treatment start (ELIGIBLE PATIENTS of the Uncommon Mutation Cohort) – Secondary objective #3: formatted table will be checked against the raw output
- Table 12-UNC. Mutations at second-line treatment start (ELIGIBLE PATIENTS of the Uncommon Mutation Cohort): [REDACTED]/another BS will independently recalculate descriptive statistics and check the algorithm for 10% of analyzed patients
- Table 18-UNC. NSCLC treatment patterns (ELIGIBLE PATIENTS of the Uncommon Mutation Cohort): [REDACTED]/another BS will independently recalculate descriptive statistics and check the algorithm for 10% of analyzed patients
- Table 31-UNC. Details of index EGFR-TKI treatment (ELIGIBLE PATIENTS of the Uncommon Mutation Cohort): [REDACTED]/another BS will independently recalculate descriptive statistics and check the algorithm for 10% of analyzed patients
- Table 34-UNC. Index EGFR-TKI therapy patterns (ELIGIBLE PATIENTS of the Uncommon Mutation Cohort): [REDACTED]/another BS will independently recalculate descriptive statistics and check the algorithm for 10% of analyzed patients

- Table 35-UNC. Response to index EGFR-TKI treatment (ELIGIBLE PATIENTS of the Uncommon Mutation Cohort) – Secondary objective #1: formatted table will be checked against the raw output

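### The SAP's BMI formula multiplies height in centimetres by 100 instead of dividing; coded as written, it puts every patient with known weight and height into one BMI class in Tables 5-UNC and 5-SEQ

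*SAP*

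**What the plan says.** SAP section 3 (Computed variables) gives the only BMI formula in either document. For the numerator, "it will be computed as “Weight” (in Kg"; the denominator is height, printed as "in centimeters) [CCPE.CCPE_height_num, CCPE_height_unit] * 100) ^ 2". The unit is not left open: "in case height is not reported in cm, a conversion will be performed". As reproduced, the expression has a closing bracket with no opening partner.

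The same paragraph then sets the classes: "underweight: BMI < 18.5, normal weight: BMI 18.5-24.9, overweight: BMI 25-29.9, obese: BMI >= 30".

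SAP section 4.1.2 uses the result in Table 5-UNC, which shows patients "by classes of BMI at start of first-line treatment". The layout in section 5.1.2 has the four classes and a row for unknown, with no numeric BMI summary. For Table 5-SEQ, section 4.2.2 says only "See corresponding table for the UNCOMMON MUTATION COHORT", so the sequencing cohort inherits the same derivation.

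**The concern.** A derivation rule in section 3 is what the programmer codes from. Here the formula and the class limits beside it are on different scales: limits of 18.5, 25 and 30 apply to kg/m², and a height in centimetres has to be divided by 100 to reach metres. The SAP multiplies.

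At stake is the BMI row of the baseline table in both cohorts. Because only class counts are displayed, an impossible BMI value would not itself appear in the output. The sole visible sign would be that all evaluable patients sit in one class.

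The targeted quality control in SAP section 6 does not reach this row. The tables to be reprogrammed or independently verified include 1, 2, 8, 10 and 12 for the uncommon mutation cohort and 1, 2, 12 and 16 for the sequencing cohort, among others, but Table 5 is on neither list. The revision history in section 7 records no change to Table 5.

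**Working it through.** **Inputs.** From SAP section 3: W = weight in kg, H = height in cm, the factor 100 with a multiplication sign, the square, and the class limits. The documents give no patient weights or heights, so the values below are assumptions for illustration. The plan states no BMI figure to reproduce.

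**Step 1: what the class limits need.** BMI = W / (H / 100)². For 65 kg and 165 cm: 65 / 1.65² = 65 / 2.7225 = 23.9, normal weight.

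**Step 2: what is printed.** One opening bracket is missing, so each place where it could go is evaluated for the same patient.

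| Reading | Formula | 65 kg, 165 cm | Class |
|---|---|---|---|
| A (natural) | W / (H × 100)² | 65 / 16,500² = 2.4 × 10⁻⁷ | underweight |
| B | (W / H × 100)² | 39.39² = 1,552 | obese |
| C | W / H × (100)² | 0.3939 × 10,000 = 3,939 | obese |

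Reading A differs from the correct value by (100 × 100)² = 10⁸, whatever the weight and height. If the factor was meant to turn metres into centimetres, the result is W / H² = 65 / 165² = 0.0024, again underweight.

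**Step 3: is this peculiar to one patient?** The three readings were evaluated over an assumed grid of weights from 30 to 200 kg and heights from 130 to 210 cm in whole units, which is 171 × 81 = 13,851 combinations.

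- A: values from 6.8 × 10⁻⁸ to 1.2 × 10⁻⁶; all 13,851 underweight.
- B: values from 204 to 23,669; all 13,851 obese.
- C: values from 1,429 to 15,385; all 13,851 obese.

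The result does not depend on the grid limits. At 165 cm, leaving the underweight class under A would take at least 18.5 × 16,500² ≈ 5.0 × 10⁹ kg. Leaving the obese class would take less than √30 × 165 / 100 ≈ 9.0 kg under B, and less than 30 × 165 / 10,000 ≈ 0.5 kg under C.

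**Step 4: the corrected formula.** 45 kg/165 cm gives 16.5 (underweight), 60 kg/165 cm gives 22.0 (normal), 75 kg/165 cm gives 27.5 (overweight) and 95 kg/170 cm gives 32.9 (obese). All four classes can be populated.

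**Step 5: class limits.** The classes end at 24.9 and 29.9 and restart at 25 and 30. An unrounded BMI of 24.95 has no class. After rounding to one decimal no gap remains, but the SAP states no rounding rule for BMI.

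**The case against.** The best answer is that this is a slip that would correct itself. The line as printed cannot be run because its brackets do not balance, so someone has to repair it, and the familiar limits in the same paragraph show the intended scale. The unmatched bracket may be an artefact of reading the PDF and should not count as a separate defect. Section 6 also provides controls that cover every table: programming and verification by a biostatistician, an independent consistency review, and this: "R-DMS will perform an overall conceptual review of results, in order to evaluate their coherence and plausibility". A baseline table with all evaluable patients underweight, or all obese, is just what such a review should notice.

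Most of that stands, and it limits the consequence. It does not remove the error. The multiplication sign is wrong under every bracket placement, and a checker who works from the SAP would be confirming against the wrong formula.

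A reader might infer that every patient would be classed wrongly. The documents do not support that. Under reading A, a truly underweight patient (45 kg, 165 cm, BMI 16.5) lands in the right class by coincidence; under B or C the same holds for a truly obese one (95 kg, 170 cm, BMI 32.9). Patients without weight or height have the unknown row. Nor can one say which single class would result without settling the bracket.

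On the class gaps, the objection is largely right. Limits written to one decimal imply rounding, so this is a clarification and not an arithmetic error.

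**Conclusion.** The formula is wrong as written. If it is coded literally, every patient with known weight and height falls into a single BMI class in Tables 5-UNC and 5-SEQ: underweight on the natural reading, obese on the other bracket placements. This rests on literal coding and on any plausible adult weight and height.

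The importance is low. A reader might infer that the reported table will be wrong, or that the study's findings are affected; neither follows. The first depends on the slip passing both the programmer and the general review. As to the second, in the text available BMI is only a descriptive baseline row. It plays no part in eligibility, time on treatment, survival or response; protocol section 9.3.3 names no covariates, and SAP section 4 plans no comparisons.

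**What to change.** In SAP section 3, replace the expression with BMI = weight (kg) / (height (cm) / 100)², with balanced brackets, and confirm that the program behind Tables 5-UNC and 5-SEQ uses it.

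As a minor clarification in the same edit, write the classes as <18.5, ≥18.5 to <25, ≥25 to <30 and ≥30, or state that BMI is rounded to one decimal before classing. Carry the choice into the Table 5-UNC layout in section 5.1.2.

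The formula correction is one line of text and the class clarification a small edit. Neither needs new data.

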- “EGFR mutations at start of second-line treatment” [Second-line treatment period / MUT2. MUT2_mut_start] includes “T790M”

Criterion 7 (UNCOMMON MUTATION COHORT). Patient has started EGFR-TKI treatment at least 12 months prior to data entry

- “Cohort” [PI. PI_coh_ty] = “Uncommon Mutation cohort” AND
- “7. Patient has started EGFR-TKI treatment at least 12 months prior to data entry” in the ELIGIBILITY CRITERIA form [EC. EC_IC_7umc] = “Yes” AND
- “7. Patient has started EGFR-TKI treatment at least 12 months prior to data entry” in the PROTOCOL DEVIATION FORM [PDF. PDF_IC7_umc] is not flagged AND
- Start date of the Index EGFR-TKI therapy (as defined in “Chapter 3”) is lower than or equal to (“Date of data collection (dd/mmm/yyyy)” [PI. PI_date_coll] – 11.50 months) (*)

This line shall start in presence of at least one uncommon/compound mutation (as described in the definition of the calculated variable “Index EGFR-TKI therapy”: see “Chapter 3”).

(*) this means that if the start date of the index EGFR-TKI therapy is 11.49 months before date of data collection, the patient violates this criterion. This tolerance window has been agreed with the Sponsor during the Data Analysis Strategic Meeting, and will not be further discussed. Only in case exact day is not known and this makes the evaluation critical with the respect to the tolerance window, then case-by-case discussion will be done with the Sponsor.

In case the Index therapy line is an EGFR-TKI given in combination with chemotherapy, a query will be raised in order to ensure that the treatment line was administered according to regular clinical practice.

Criterion 7 (SEQUENCING COHORT). Patient has started osimertinib treatment at least 10 months prior to data entry

- “Cohort” [PI. PI_coh_ty] = “Sequencing cohort” AND
- “7. Patient has started osimertinib treatment at least 10 months prior to data entry” in the ELIGIBILITY CRITERIA form [EC. EC_IC_7sc] = “Yes” AND
- “7. Patient has started osimertinib treatment at least 10 months prior to data entry” in the PROTOCOL DEVIATION FORM [PDF. PDF_IC7_sc] is not flagged AND
- Start date of the Index EGFR-TKI therapy (as defined in “Chapter 3”) is lower than or equal to (“Date of data collection (dd/mmm/yyyy)” [PI. PI_date_coll] – 9.50 months) (*)

This line shall start in presence of at least one common mutation (as described in the definition of the calculated variable “Index EGFR-TKI therapy”: see “Chapter 3”).

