- For UNCOMMON MUTATION COHORT, it will be defined according to the fields **[First-line treatment period / MUT1. MUT1_unc, MUT1_unc_ex20_sp, MUT1_unc_sp]**.
- For SEQUENCING COHORT, it will be defined according to the field **[First-line treatment period / MUT1. MUT1_seq]**.

EGFR mutational status at second-line treatment start

It will be defined according to the following fields recorded in the MUTATIONS form of the [**Second-line treatment period**] time period (when applicable); for UNCOMMON MUTATION COHORT, only patients with Number of NSCLC treatment lines (as defined before) >1 should be considered:

- if “Was mutational status re-evaluated at start of second-line treatment?” [**MUT2. MUT2_reeval**] = “No” OR if “Any changes in EGFR mutations at start of second-line treatment with respect to start of first-line treatment?” [**MUT2. MUT2_changes**] = “UNK”, patients will be classified as “Unknown EGFR mutational status”
- if “Any changes in EGFR mutations at start of second-line treatment with respect to start of first-line treatment?” [**MUT2. MUT2_changes**] = “No”, then the patient’s EGFR mutational status at second-line treatment start will be imputed as the same patient’s EGFR mutational status at first-line treatment start (as defined before)
- if “Any changes in EGFR mutations at start of second-line treatment with respect to start of first-line treatment?” [**MUT2. MUT2_changes**] = “Yes”, then the patient’s EGFR mutational status at second-line treatment start will be retrieved from the fields [**MUT2. MUT2_mut_start**, **MUT2_mut_start_ex20_sp**, **MUT2_mut_start_sp**, **MUT2_concom_mut_start**]

Acquired EGFR mutations at second-line treatment start

For both cohorts, the mutations found at start of second-line treatment (i.e. the options selected in the field [**MUT2. MUT2_mut_start**]) will be compared to the mutations found at start of first-line treatment (i.e. the options selected in the field [**MUT1. MUT1_mut_unc**] for the UNCOMMON MUTATION COHORT, or in the field [**MUT1. MUT1_mut_seq**] for the SEQUENCING COHORT). The mutations found at start of second-line treatment that were not present at first-line treatment start will be classified as acquired EGFR mutations.

EGFR mutational status at second-line treatment stop/end of observation

It will be defined according to the following fields recorded in the MUTATIONS form of the [**Second-line treatment period**] time period (when applicable):

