- if “Was mutational status re-evaluated at at stop of second-line treatment (or within end of observation, in case second-line treatment was not discontinued)?” [**MUT2. MUT2_reeval_stop**] = “No” OR if “Any changes in EGFR mutations with respect to start of second-line treatment?” [**MUT2. MUT2_changes_stop**] = “UNK”, patients will be classified as “Unknown EGFR mutational status”
- if “Any changes in EGFR mutations with respect to start of second-line treatment?” [**MUT2. MUT2_changes_stop**] = “No”, then the patient’s EGFR mutational status at second-line treatment stop/end of observation will be imputed as the same patient’s EGFR mutational status at second-line treatment start (as defined before)
- if “Any changes in EGFR mutations with respect to start of second-line treatment?” [**MUT2. MUT2_changes_stop**] = “Yes”, then the patient’s EGFR mutational status at second-line treatment stop/end of observation will be retrieved from the fields [**MUT2. MUT2_mut_stop**, **MUT2_mut_stop_ex20_sp**, **MUT2_mut_stop_sp**, **MUT2_concom_mut_stop**]

Acquired EGFR mutations at second-line treatment stop/end of observation

For both cohorts, the mutations found at stop of second-line treatment/end of observation (i.e. the options selected in the field [**MUT2. MUT2_mut_stop**]) will be compared to the mutations found at start of second-line treatment (i.e. the options selected in the field [**MUT2. MUT2_mut_start**]). The mutations found at second-line treatment stop/end of observation that were not present at start of second-line treatment will be classified as acquired EGFR mutations.

Classification of EGFR uncommon mutations (according to Yang's classification) for exploratory analyses

According to the MUTATIONS form, considering the EGFR mutational status at first- and second-line treatment start (but considering only lines containing EGFR-TKIs), the following definitions will be applied to classify patients' mutational status with respect to EGFR gene:

- **T790M-positive:** patients having T790M at start of either first- or second-line EGFR-TKI, but excluding patients developing acquired T790M at second-line osimertinib start;
- **Exon 20 insertion-positive:** patients having any type of exon 20 insertion at start of either first- or second-line EGFR-TKI, excluding patients included in group "a");

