- absolute and relative frequency of “Methodology used for mutation testing”, with details of ARMS, sequencing, NGS (according to the fields [*Second-line treatment period / MUT2. MUT2_meth_start, MUT2_meth_start_sp, MUT2_meth_ARMS, MUT2_meth_ARMS_sp, MUT2_meth_seq, MUT2_meth_seq_sp, MUT2_meth_NGS, MUT2_meth_NGS_sp*])

Descriptives and percentages will be calculated over the number of ELIGIBLE PATIENTS in the cohort, considering only patients with Number of NSCLC treatment lines >1 (see “Computed variables” chapter) with “Was mutational status re-evaluated at start of second-line treatment” [*Second-line treatment period / MUT2. MUT2_reeval*] = “Yes”.

[figure not shown]

Table 15-UNC. Mutations at second-line treatment stop/end of observation (ELIGIBLE PATIENTS of the Uncommon Mutation Cohort)

The table will provide:

- absolute and relative frequency of patients according to EGFR mutational status at second-line treatment stop/end of observation (see “Computed variables” chapter);
- absolute and relative frequency of patients according to Classification of EGFR uncommon mutations at second-line treatment stop/end of observation (see “Computed variables” chapter);
- absolute and relative frequency of patients according to acquired EGFR mutations at second-line treatment stop/end of observation (see “Computed variables” chapter);
- absolute and relative frequency of patients according presence/absence of other mutated genes and detail of mutations at second-line treatment stop/end of observation (according to the fields [*Second-line treatment period / MUT2. MUT2_oth_gene_stop_YN* (*), *MUT2_oth_gene_stop, MUT2_oth_gene_stop_sp*]).

(*) in case [*MUT2_oth_gene_stop_YN*] = “No”, then the patient’s mutational status for other genes at second-line treatment stop/end of observation will be imputed as the same patient’s mutational status for other genes at second-line treatment start.

Descriptives and percentages will be calculated over the number of ELIGIBLE PATIENTS in the cohort, considering only patients with Number of NSCLC treatment lines >1 (see “Computed variables” chapter) with “Was mutational status re-evaluated at stop of second-line treatment [...]” [*Second-line treatment period / MUT2. MUT2_reeval_stop*] = “Yes”.

Table 16-UNC. Approaches for detection of mutations at second-line treatment stop/end of observation (ELIGIBLE PATIENTS of the Uncommon Mutation Cohort) – Secondary objective #3

The table will provide:

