	L858R	xxx (xx.x%)
	L858X (with X being unequal to R)	xxx (xx.x%)
	T790M de novo	xxx (xx.x%)
	G719X	xxx (xx.x%)
	L861Q	xxx (xx.x%)
	S768I	xxx (xx.x%)
	E709X	xxx (xx.x%)
	L747P/S	xxx (xx.x%)
	Q787Q	xxx (xx.x%)
	Exon 20 insertion (*)	xxx (xx.x%)
	Other EGFR mutation(s) (*)	xxx (xx.x%)
	Unknown EGFR mutational status	xxx (xx.x%)
Classification of EGFR uncommon mutations at second-line treatment stop/end of observation	T790M-positive	xxx (xx.x%)
	Exon 20 insertion-positive	xxx (xx.x%)
	Major uncommon mutations	xxx (xx.x%)
	Others	xxx (xx.x%)
	Compound mutations	xxx (xx.x%)

(*) listing might be provided depending on the number of cases observed.

ELIGIBLE PATIENTS with >1 NSCLC line (N=xxx)		
Acquired EGFR mutations at second-line treatment stop/end of observation	Del19	xxx (xx.x%)
	L858R	xxx (xx.x%)

ELIGIBLE PATIENTS with >1 NSCLC line (N=xxx)		
Other new genes alterations at second-line treatment stop/end of observation?	Yes	xxx (xx.x%)
	No	xxx (xx.x%)
	UNK	xxx (xx.x%)
Other known genes alterations	ALK	xxx (xx.x%)
	HER2	xxx (xx.x%)
	KRAS	xxx (xx.x%)
	MET amplification	xxx (xx.x%)
	PI3KCA	xxx (xx.x%)
	PTEN	xxx (xx.x%)
	ROS1	xxx (xx.x%)
	Other gene(s) mutated (*)	xxx (xx.x%)

(*) listing might be provided depending on the number of cases observed.

Table 16-UNC. Approaches for detection of mutations at second-line treatment stop/end of observation (ELIGIBLE PATIENTS of the Uncommon Mutation Cohort) – Secondary objective #3

		ELIGIBLE PATIENTS with >1 NSCLC line with re-evaluated mutational status (N=xxx)
Biologic sample(s) used for mutation testing	Tissue, Histological sample (solid biopsy)	xxx (xx.x%)
	Cytological sample	xxx (xx.x%)
	Blood (liquid biopsy)	xxx (xx.x%)
	Other (*)	xxx (xx.x%)
	UNK	xxx (xx.x%)
Methodology used for mutation testing	Amplification Refractory Mutation System (ARMS)	xxx (xx.x%)
	- ADx	xxx (xx.x%)
	- Qiagen	xxx (xx.x%)
	- Roche	xxx (xx.x%)
	- Super ARMS	xxx (xx.x%)
	- Other (*)	xxx (xx.x%)
	- UNK	xxx (xx.x%)
	ddPCR	xxx (xx.x%)
	BEAMing	xxx (xx.x%)
	Sequencing	xxx (xx.x%)
	- Sanger sequencing	xxx (xx.x%)
	- Pyrosequencing	xxx (xx.x%)
	- Other (*)	xxx (xx.x%)
	- UNK	xxx (xx.x%)
	Next-Generation Sequencing (NGS)	xxx (xx.x%)
	- Targeted NGS	xxx (xx.x%)
	- Whole-exome sequencing	xxx (xx.x%)
	- Whole-genome sequencing	xxx (xx.x%)
	- Other (*)	xxx (xx.x%)
	- UNK	xxx (xx.x%)
	Other	xxx (xx.x%)
	UNK	xxx (xx.x%)

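### Uncommon mutation cohort: a patient re-tested at second-line stop with no change is reported as of unknown EGFR status if second-line start was untested

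*SAP*

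**What the plan says.** SAP section 3 derives EGFR mutational status at three time points; two matter here.

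- **Second-line start.** If the item "Was mutational status re-evaluated at start of second-line treatment" is answered 'No', or the question on changes since first line is answered 'UNK', "patients will be classified as “Unknown EGFR mutational status". First-line status is copied only when the patient was re-tested and no change was recorded.
- **Second-line stop or end of observation.** If there was no re-test, or the question on changes (`MUT2_changes_stop`) is answered 'UNK', the status is again unknown. If the answer is 'No', the "EGFR mutational status at second-line treatment stop/end of observation will be imputed as the same" as at second-line start. If the answer is 'Yes', "EGFR mutational status at second-line treatment stop/end of observation will be retrieved from the fields" that list the mutations found at stop.

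SAP section 4.1.3 limits Table 15-UNC to patients with more than one line for whom "Was mutational status re-evaluated at stop of second-line treatment" is answered 'Yes'. The layout in SAP section 5.1.3 nevertheless has a row "Unknown EGFR mutational status".

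**The concern.** Table 15-UNC describes the tumour at the end of second line in patients who were tested then. For a patient whose second-line-start status is unknown, the stop rule gives a known result only if something changed. If nothing changed, the patient inherits the label 'Unknown', although a test was done at stop and a mutation is on record from first line.

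At stake is the description of mutations that persist: their rows would be too low, with the shortfall in the 'Unknown' row. The same derived status feeds the classification of uncommon mutations at stop, so a patient could also be put in the wrong class.

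**Working it through.** The plan states no figure on this point, so the check is to apply its rules as written.

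**Step 1: can the situation arise?** Yes. Criterion 5 for the uncommon cohort and the definition of index therapy accept a mutation recorded at first-line start even when the index EGFR-TKI is second-line, so a re-test at second-line start is not required. The layout of Table 12-UNC has an 'Unknown' row for that time point, so the plan expects such patients.

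**Step 2: run the rules for a patient tested at stop.** The copy instruction reads "will be imputed as the same patient’s EGFR mutational status at second-line treatment start (as defined before". It refers back to the computed status, which includes the label 'Unknown'.

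| Second-line start | Changes at stop: No | Yes | UNK |
|---|---|---|---|
| Not tested (status Unknown) | Unknown | mutations listed at stop | Unknown |
| Tested, changes UNK (status Unknown) | Unknown | mutations listed at stop | Unknown |
| Tested, status known | start status | mutations listed at stop | Unknown |

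The fault is in the first two 'No' cells.

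**Step 3: the class at stop.** In SAP section 3, 'Others' is everyone not in the T790M, exon 20 insertion or major uncommon groups. At second-line start the classification is limited to re-tested patients, and patients without mutations are kept out of 'Others'. At stop the only filters are more than one line and a re-test at stop. A patient with a copied 'Unknown' passes both, meets none of the first three definitions and, read literally, lands in 'Others'.

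**Step 4: the sequencing cohort.** Criterion 6 requires T790M among the mutations recorded at second-line start, so the start status is known and the fault cannot occur.

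**Step 5: size, by illustration only.** Let u be the share of patients tested at stop who were not tested at second-line start, and c the share with a change at stop. Neither is in the documents. I assume u = 10% to 50% and c = 20% to 60%, c the same whether or not start was tested, and no 'UNK' answers at stop. Per 100 patients tested at stop:

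- wrongly unknown = 100 × u × (1 − c)
- unchanged, as printed = 100 × (1 − u) × (1 − c), against a true 100 × (1 − c)
- changed, as printed = 100 × c, which is correct

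| u | c | Wrongly unknown | Unchanged: printed / true | Changed: printed / true |
|---|---|---|---|---|
| 10% | 60% | 4 | 36 / 40 | 60 / 60 |
| 10% | 40% | 6 | 54 / 60 | 40 / 40 |
| 30% | 40% | 18 | 42 / 60 | 40 / 40 |
| 50% | 60% | 20 | 20 / 40 | 60 / 60 |
| 50% | 20% | 40 | 40 / 80 | 20 / 20 |

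'Unchanged' and 'changed' describe patients here; the table itself lists individual mutations.

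**The case against.** The strongest objection is that the trigger depends on an eCRF that is not among the documents. The question at stop asks about change since second-line start. With no test at that point, a site may well answer 'UNK', and the patient then becomes unknown through a different branch. The eCRF or the Data Validation Plan might also block or query the combination. This stands as a limit on how often the copy rule acts. It does not remove the gap: the SAP gives no exception, and the 'UNK' branch also labels a patient tested at stop as unknown.

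Second, the 'Unknown' row is not wrong in itself, since 'UNK' answers at stop belong there. That is fair, but it means wrongly labelled patients cannot be told apart from the others in the row.

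Third, a reader might infer that resistance or changed profiles are overstated. The documents do not support this. Percentages in Table 15-UNC use all patients re-tested at stop, with the unknowns shown. No planned table reports a changed share among known results only. Acquired mutations are derived separately, by comparing the raw fields at stop and start, so the copied status does not enter them.

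Fourth, labelling an untested start as unknown looks deliberate, and 'no change since an untested start' does not by itself establish the first-line status. This also stands, and is why the repair needs a site query.

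**Conclusion.** The point holds in a limited form. As written, the stop rule can report a patient of the uncommon mutation cohort as unknown although the tumour was tested at stop and no change was recorded. Persisting mutations are then under-reported in Table 15-UNC, and the patient may be misplaced in 'Others' at stop. Table 17-UNC is laid out by these classes, but its descriptive text is not visible, so an effect there cannot be confirmed.

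The number affected cannot be derived; the range of 4 to 40 per 100 rests wholly on the assumptions in the working.

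Little else depends on it. Table 15-UNC is descriptive and carries no objective label. Secondary objective #3 uses raw fields in Table 16-UNC, and protocol section 9.7 plans the tabulation of resistance mutations only for the sequencing cohort. Time on treatment and overall survival do not use this variable. The correction is worth making because it is cheap, not because a main result is at risk.

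**What to change.** In SAP section 3, amend the status at second-line stop for patients with `MUT2_reeval_stop` = 'Yes':

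1. Whenever `MUT2_mut_stop` is completed, take the status from it, whatever the answer on changes. This also covers sites that answer 'UNK'.
2. If that field is blank, `MUT2_changes_stop` = 'No', and the second-line-start status is unknown because `MUT2_reeval` = 'No', use the first-line-start status as the last known status, but only after a site query confirms it. Footnote in Table 15-UNC how many patients this concerns.
3. Leave all other such patients as unknown, and keep them out of the 'Others' class at stop.

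Step 2 is needed because the present rule reads `MUT2_mut_stop` only for 'Yes', so the field may be empty for 'No'.

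The cost is a short SAP edit, a few lines of code and a few queries. The downside is small: step 2 assumes that 'no change' refers to the last known result, which the query is there to confirm.
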